6.2.13. Planned Analysis

The final myelosuppression analysis will be conducted after all patients have had the opportunity to receive at least 12 weeks of treatment (ie, randomized induction treatment part of the study). All study data collected through the time of the final myelosuppression analysis data cut will be included. This includes, but is not limited to the final myelosuppression analysis, interim ORR analysis based on investigator assessment, and interim PFS/OS analysis.

The time when at least 80% of patients having experienced a progression will be considered to be final PFS analysis. Patients will be followed for survival until at least 70% of the patients have died at which time an end of study analysis for OS will be conducted. Reported results, except the myelosuppression analyses, will be cumulative in nature, including all data collected during the entire study; the myelosuppression analyses will be complete at the final myelosuppression analysis and no additional data will be expected. Additional PFS/OS analyses may be done with the timing to occur between the final myelosuppression analysis and study completion.

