##### 8.4.5.2. Modification of Etoposide and Carboplatin Dosing

Patients should meet the laboratory parameter requirements outlined in Section 10.3.2 before initiation of Cycle 2 and each subsequent cycle of E/P therapy. All nonhematologic drug-related toxicities (except alopecia) should have resolved to Grade 1 or baseline before initiation of the next cycle of E/P therapy.

Dose adjustments are to be made according to the organ system showing the greatest degree of drug-related toxicity. Toxicities will be graded using NCI CTCAE, Version 4.03. Initiation of the next cycle of trilaciclib or placebo + E/P therapy may be delayed by no more than 9 weeks to allow recovery from toxicity due to the chemotherapy agents. A treatment delay of > 9 weeks due to trilaciclib or placebo + E/P toxicity will lead to discontinuation of trilaciclib or placebo + E/P therapy.

No more than 2 dose reductions of E/P in total are allowed for any patient. Simultaneous reduction in the doses of etoposide and carboplatin will count as 1 dose reduction. Toxicity

that requires dose reduction more than twice will lead to discontinuation of trilaciclib or placebo + E/P therapy. Under this circumstance, administration of trilaciclib or placebo should also be discontinued. All dose reductions are permanent and no dose increases are allowed.

Since fatigue can be a symptom of cancer progression, dose reduction will only be performed if it is deemed to be drug-related in the opinion of the investigator.

The dose reductions in [Table 8-1](#) will be utilized for the purpose of dose modifications for toxicity.

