#### 10.4. **Last Induction Cycle – Day 22**

On Day 22 of the last induction cycle, patients will return to the clinic for ECG assessment and collection of a blood sample for hematology tests.

- If the patient continues directly into maintenance without interruption, then the hematology and ECG assessments will be performed as part of the Day 1 assessments in the first cycle of atezolizumab maintenance.
- If atezolizumab is held or discontinued for any reason after the last cycle of trilaciclib/placebo with carboplatin and etoposide, the patient should return to the clinic at the end (eg, Day 22) of this last induction cycle for hematology and ECG assessments.

Adverse events and concomitant medications will be monitored throughout the study. AEs and concomitant medications will be collected through 30 days after the last dose of study drug; SAEs and AESI will be collected through 90 days after the last dose of study drug.

For patients who have a confirmed CR, it is strongly recommended that they receive PCI after completion of chemotherapy. Patients with a confirmed partial response should also consider PCI after completion of chemotherapy based on the investigator's judgment.

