#### **10.6. Post-Treatment Visits**

Patients will return to the study center for post-treatment visits at 30 (+3) days and at 90 (+7) days after the last dose of study drug. The following procedures will be performed at these visits:

- ECOG performance status evaluation
- Physical examination
- Weight and vital signs measurements
- Clinical chemistry, hematology, and urinalysis tests
- TSH, free T4, and free T3 tests

- Pregnancy test
- Tumor assessment (obtain tumor assessment by CT scan or MRI for patients who have not progressed at the time of study drug discontinuation [every 2 months (approximately  $60 \pm 7$  days) until the occurrence of progressive disease or study completion]; see details in Section 11.1.1) after every even cycle for the first 9 months of the study and after every third cycle thereafter
- Brain scan with contrast (obtain brain scans by MRI or CT for patients who have not progressed at the time of study drug discontinuation [may be performed within 4 weeks])
- [REDACTED]
- Plasma PK sample for measurement of atezolizumab concentration (30 [+3] and 90 [+7] days after the last dose of study drug)
- [REDACTED]
- Immunologic markers blood sample collection (90 [+7] days after the last dose of study drug, only)

AEs and concomitant medications will be collected through 30 days after the last dose of study drug; SAEs and AESI will be collected through 90 days after the last dose of study drug.

After completing the post-treatment visits, patients will enter the long-term Survival Follow-up Phase.

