At the time of performing the primary and secondary myelosuppression analyses, all patients will have completed the randomized induction treatment part of the study and will have discontinued trilaciclib or placebo. However, patients may still be in the atezolizumab monotherapy maintenance part of the study or being followed for survival. This will ensure that this amendment will not incur any potential operational bias for the PFS/OS analysis results.

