#### 13.2.2.2. Final Analysis

The final analysis will be conducted after all patients have had the opportunity to receive at least 12 weeks of treatment (ie, randomized induction treatment part of the study). All study data collected through the time of the final analysis data cut, will be included in the final analysis. This includes, but is not limited to, the final myelosuppression analysis, final ORR analysis, and interim PFS/OS analyses.

At the time of the final analysis, the sponsor will be unblinded; however, investigators and patients will remain blinded.

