5. PRIMARY AND SECONDARY ENDPOINTS

The following general definitions will be applied to all endpoints derivation unless otherwise specified.

Term	Definition
Severe Neutropenia (SVN)	ANC lab value that meets the common terminology criteria for adverse events (CTCAE) criteria for \geq Grade 4 toxicity
Cycle baseline	The last non-missing value within the window starting from 3 days prior to the date/time of study drug administration on Day 1 of Cycle 1 and 1 day prior to Day 1 of each subsequent cycle (i.e. Cycle 2, Cycle 3, etc.); must be prior to the time of study drug administration
Cycle nadir	The lowest value for a given hematologic parameter that occurs between start of cycle and end of cycle and is less than the cycle baseline.
Duration of cycle	Total number of days from start of cycle to end of cycle, that is, date of end of a cycle - date of start of cycle + 1.
End of cycle*	Day 1 of the subsequent cycle. For example, the end of cycle for Cycle 1 is Day 1 of Cycle 2. For the last induction cycle (where no subsequent maintenance cycle is given), the end of cycle will be defined as Day 36 after the first dose of the cycle. For the last maintenance cycle, the end of cycle will be defined as Day 30 after the first dose of the cycle.
Start of cycle	Day 1 of each cycle starts with the administration of study drug(s) (etoposide, carboplatin, atezolizumab, or trilaciclib)
Start of study	Date of randomization
Study baseline	The last non-missing value prior to, or on the date of administration of study drug(s) (etoposide, carboplatin, atezolizumab, or trilaciclib); must be prior to the time of study drug administration
Change from baseline	Calculated as the post-baseline value minus the baseline value. If the baseline value is missing for a particular endpoint, change from baseline will be missing.
Induction treatment period	Between the date of randomization and end of cycle for the last Induction cycle.
Maintenance treatment period	Between the date of Day 1 of the first maintenance cycle and end of cycle for the last Maintenance cycle.
Overall treatment period	Between the date of randomization and end of cycle for the last cycle.

* For various hematologic parameter analyses, the last assessment prior to end of cycle will be utilized in the analyses. Situations where this applies will be indicated as such.

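### Could the 12-week rule cut off the final myelosuppression analysis before induction has ended?

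*SAP*

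**What the plan says.** SAP 6.2.13 sets the timing: "The final myelosuppression analysis will be conducted after all patients have had the opportunity to receive at least 12 weeks of treatment". A parenthesis in the same sentence equates this with the randomised induction part. Protocol 13.2.2.2 gives the same rule and adds: "At the time of the final analysis, the sponsor will be unblinded; however, investigators and patients will remain blinded". The SAP treats this as the only look at these endpoints: "the myelosuppression analyses will be complete at the final myelosuppression analysis and no additional data will be expected".

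The introduction to Protocol Section 13 describes the position at these analyses: "all patients will have completed the randomized induction treatment part of the study and will have discontinued trilaciclib or placebo".

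The endpoint window is defined separately. In SAP Section 5 the induction treatment period runs from randomisation to the end of the last induction cycle. If maintenance follows, that is Day 1 of the next cycle. If it does not, "the end of cycle will be defined as Day 36 after the first dose of the cycle".

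Three scheduling provisions matter:
- On Day 22 of the last induction cycle (Protocol 10.4) patients "return to the clinic for ECG assessment and collection of a blood sample for hematology tests". Those going straight into maintenance have this done at maintenance Day 1.
- Protocol 10.6 has "post-treatment visits at 30 (+3) days and at 90 (+7) days after the last dose of study drug", with hematology at both.
- Under Protocol 8.4.5.2 the next cycle "may be delayed by no more than 9 weeks to allow recovery from toxicity".

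**The concern.** The minimum equals four cycles with no slippage, while the endpoint window can run past it. A patient without maintenance is still inside the window for about two weeks after the minimum, and a delayed patient for as long as the delay. A scheduled blood count can fall in that stretch.

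Occurrence of Grade 4 neutropenia, RBC transfusions on or after Week 5, G-CSF use and MAHE are all counted over the whole induction period. The sponsor is unblinded at this analysis and no later myelosuppression data are expected, so events missed at the cut would stay missed. If delays were more common on placebo, the loss would fall more on that arm and shrink the treatment difference.

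The models would not fully absorb it. The offset for Grade 4 neutropenia and G-CSF is the log number of induction cycles, so a patient cut off inside Cycle 4 counts as four full cycles. For transfusions and MAHE it is log induction duration, which could include days not yet observed.

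**Working it through.** **Calendar, in days after first dose**

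- Minimum: 12 × 7 = 84 days; four undelayed cycles: 4 × 21 = 84. The plan's equation of 12 weeks with induction reproduces.
- Cycle 4 Day 1 = 3 × 21 = 63; Cycle 4 Day 22 = 63 + 21 = 84.
- Undelayed, maintenance follows: induction ends at day 84. The minimum reaches it.
- Undelayed, no maintenance: 63 + 36 = 99. Gap 15 days.
- Last dose without maintenance (Cycle 4 Day 3) = 65; 30 (+3) day visit = 95 to 98. This is the only scheduled hematology after the minimum and inside the window for an undelayed patient.
- Undelayed, stopping after Cycle 3 without maintenance: 42 + 36 = 78, inside the minimum.
- Each day of delay adds a day.
- Cycle 1 with a maximal 9-week delay ends at 21 + 63 = 84, so Cycle 1 duration of severe neutropenia is complete.
- Dose reductions compare each cycle's dose with the previous one (SAP 5.2.1.4), so they are settled once Cycle 4 is dosed.

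**How many patients**

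From the documents: 106 patients, 1:1, 12 months of accrual. Assumed, because the documents give no figures: uniform accrual, 80% entering maintenance, one delay of 1 to 4 weeks in 40% of placebo and 20% of trilaciclib patients. Simulation of 20,000 trials; expected number short of the SAP end of induction:

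| Cut and assumptions | Short of end (of 106) |
|---|---|
| Last first dose + 84 days, base case | 2.9 (1.7 placebo, 1.1 trilaciclib) |
| Same, no delays | 1.1 |
| Same, delays of 1 to 9 weeks | 4.4 |
| Same, 30% delayed in each arm | 2.8 (1.4, 1.4) |
| No cut before the last trilaciclib/placebo dose in any patient, base case | 2.7 |
| Same, delays of 1 to 9 weeks | 2.5 |
| Same, base delays, 60% / 95% to maintenance | 3.7 / 2.0 |

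In the first row about 90% of the affected patients have finished Cycle 4 dosing, and 1.6 are past Cycle 4 Day 15. The arm imbalance comes only from the assumed 40%/20% split.

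**Effect on occurrence of Grade 4 neutropenia**

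Inputs: 45% versus 11% (SAP 2.3), 53 per arm, exact enumeration of a pooled z-test as a stand-in for the modified Poisson model. If a share q of events in affected patients is lost, the rates become 0.45 × (1 − q × 1.72/53) and 0.11 × (1 − q × 1.14/53), where 1.72 and 1.14 are the unrounded first-row counts. Expected events at stake: 1.72 × 0.45 + 1.14 × 0.11 = 0.90.

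| Loss | Rates | Power, 1-sided 0.025 | Power, 1-sided 0.0125 |
|---|---|---|---|
| None | 45.0% / 11.0% | 98.5% | 96.9% |
| q = 0.25 | 44.6% / 10.9% | 98.4% | 96.7% |
| q = 1 | 43.5% / 10.8% | 98.0% | 96.0% |

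SAP 6.2.7.1.4 tests this hypothesis alone, after Cycle 1 duration, so it gets the full 0.025; 0.0125 is the sizing level. The loss is 0.1 to 0.5 points at 0.025 and 0.2 to 0.9 points at 0.0125.

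**The case for a change.** The strongest counter-argument is that the Protocol Section 13 statement explains the amendment and is not the timing rule. Stopping trilaciclib or placebo on Cycle 4 Day 3 is also not the same as reaching the SAP's end of cycle, and the SAP supersedes the protocol where analyses differ. All three points are fair. But the statement sets two conditions, completing induction and stopping blinded drug, and Protocol 13.5 runs induction to the end of the last cycle. If completion carries that meaning, which no sentence says outright, the number cut short is zero. The SAP says nothing contrary, so precedence is not clearly engaged.

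Delays might also be worse than assumed. If every late enrollee had a 9-week delay and no maintenance, the gap would be 63 + 15 = 78 days, or 78/365 = 21% of patients. Taking 22% of patients with a quarter of their events lost, and 50 per arm at 0.0125, power falls from 95.2% to 93.4%, or to 92.1% if only placebo is affected. It stays above 90%, and the requirement that blinded drug has stopped excludes much of that case.

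The offset point stands but is slight: for an undelayed patient at most 99 − 84 = 15 days would be unobserved, and stopping the duration at the data cut is the natural handling. SAP 6.2.7.1.5 describes the patients to be imputed as not completing four cycles in one place and having fewer than four in another; both can be read as fewer than four cycles received. The effect on transfusions, G-CSF and MAHE was not computed; the same few patients are involved.

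**Conclusion.** No change follows. The calendar observation is right, but limited to patients with four cycles and no maintenance and to patients with delays; an undelayed patient going straight to maintenance is covered. SAP 6.2.13 read with Protocol Section 13 and 13.5 already points to a cut after induction is complete. What is left is a missing cross-reference to the SAP Section 5 end of cycle, which analysts would supply when fixing the cut date.

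Even on the strictest reading, about 2 to 3 of 106 patients in the base case (1.1 to 4.4 across the scenarios) lose some late Cycle 4 follow-up. Power for occurrence of Grade 4 neutropenia drops by 0.1 to 0.5 points at the 1-sided 0.025 used in this SAP. Cycle 1 duration is untouched and dose reductions essentially so. These counts rest on assumed delay and maintenance rates and uniform accrual, and no direction of bias can be claimed without an assumed difference in delays between arms. Following the plan as written would give sound results and the same conclusion.

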7. CHANGE FROM THE PROTOCOL

The endpoints and analyses listed below are based on the Statistics Section in the Protocol Amendment 2, dated 14 September 2018. The list displays the changes from the initial analysis indicated in the protocol.

- [REDACTED]
- [REDACTED]
- [REDACTED]
- [REDACTED]
- [REDACTED]
- [REDACTED]
- [REDACTED]
- [REDACTED]

AST	>ULN – 3.0 x ULN	>3.0 – 5.0 x ULN	>5.0 – 20.0 x ULN	>20.0 x ULN	-
Bilirubin	>ULN – 1.5 x ULN	>1.5 – 3.0 x ULN	>3.0 – 10.0 x ULN	>10.0 x ULN	-
Calcium (Hypercalcemia)	Corrected serum calcium of >ULN – 11.5 mg/dL; >ULN – 2.9 mmol/L; Ionized calcium >ULN - 1.5 mmol/L	Corrected serum calcium of >11.5 – 12.5 mg/dL; >2.9 – 3.1 mmol/L; Ionized calcium >1.5 - 1.6 mmol/L	Corrected serum calcium of >12.5 – 13.5 mg/dL; >3.1 – 3.4 mmol/L; Ionized calcium >1.6 - 1.8 mmol/L	Corrected serum calcium of >13.5 mg/dL; >3.4 mmol/L; Ionized calcium >1.8 mmol/L	-
Calcium (Hypocalcemia)	Corrected serum calcium of <LLN – 8.0 mg/dL; <LLN – 2.0 mmol/L; Ionized calcium <LLN - 1.0 mmol/L	Corrected serum calcium of <8.0 – 7.0 mg/dL; <2.0 – 1.75 mmol/L; Ionized calcium <1.0 - 0.9 mmol/L	Corrected serum calcium of <7.0 – 6.0 mg/dL; <1.75 – 1.5 mmol/L; Ionized calcium <0.9 - 0.8 mmol/L	Corrected serum calcium of <6.0 mg/dL; <1.5 mmol/L; Ionized calcium <0.8 mmol/L	-
CK	>ULN – 2.5 x ULN	>2.5 x ULN – 5 x ULN	>5 x ULN – 10 x ULN	>10 x ULN	-
Creatinine	>1 – 1.5 x baseline; >ULN – 1.5 x ULN	>1.5 – 3.0 x baseline; >1.5 – 3.0 x ULN	>3.0 x baseline; >3.0 – 6.0 x ULN	>6.0 x ULN	-
GGT	>ULN – 2.5 x ULN	>2.5 – 5.0 x ULN	>5.0 – 20.0 x ULN	>20.0 x ULN	-
Glucose (Hyperglycemia)	Fasting glucose value >ULN – 160 mg/dL; Fasting glucose value >ULN – 8.9 mmol/L	Fasting glucose value >160 – 250 mg/dL; Fasting glucose value >8.9 – 13.9 mmol/L	Fasting glucose value >250 – 500 mg/dL; Fasting glucose value >13.9 – 27.8 mmol/L	Fasting glucose value >500 mg/dL; Fasting glucose value >27.8 mmol/L	-
Glucose (Hypoglycemia)	<LLN – 55 mg/dL; <LLN – 3.0 mmol/L	<55 – 40 mg/dL; <3.0 – 2.2 mmol/L	<40 – 30 mg/dL; <2.2 – 1.7 mmol/L mmol/L	<30 mg/dL; <1.7 mmol/L	-

Parameter	Grade				
	1	2	3	4	5
Hemoglobin	<LLN – 10.0 g/dL; <LLN – 6.2 mmol/L; <LLN – 100 g/L	<10.0 – 8.0 g/dL; <6.2 – 4.9 mmol/L; <100 – 80 g/L	<8.0 g/dL; <4.9 mmol/L; <80 g/L	-	-
Lipase increased	>ULN - 1.5 x ULN	>1.5 - 2.0 x ULN	>2.0 - 5.0 x ULN	>5.0 x ULN	-
Potassium (Hyperkalemia)	>ULN – 5.5 mmol/L	>5.5 – 6.0 mmol/L	>6.0 – 7.0 mmol/L	>7.0 mmol/L	-
Potassium (Hypokalemia)	<LLN – 3.0 mmol/L	-	<3.0 – 2.5 mmol/L	<2.5 mmol/L	-
Lymphocyte	<LLN – 800/mm ³ ; <LLN – 0.8 x 10 ⁹ /L	<800 – 500/mm ³ ; <0.8 – 0.5 x 10 ⁹ /L	<500 – 200/mm ³ ; <0.5 – 0.2 x 10 ⁹ /L	<200/mm ³ ; <0.2 x 10 ⁹ /L	-
ANC	<LLN – 1500/mm ³ ; <LLN – 1.5 x 10 ⁹ /L	<1500 – 1000/mm ³ ; <1.5 – 1.0 x 10 ⁹ /L	<1000 – 500/mm ³ ; <1.0 – 0.5 x 10 ⁹ /L	<500/mm ³ ; <0.5 x 10 ⁹ /L	-
Phosphates	<LLN – 2.5 mg/dL; <LLN – 0.8 mmol/L	<2.5 – 2.0 mg/dL; <0.8 – 0.6 mmol/L	<2.0 – 1.0 mg/dL; 0.6 – 0.3 mmol/L	<1.0 mg/dL; <0.3 mmol/L	-
Platelet Count	<LLN – 75,000/mm ³ ; <LLN – 75.0 x 10 ⁹ /L	<75,000 – 50,000/mm ³ ; <75.0 – 50.0 x 10 ⁹ /L	<50,000 – 25,000/mm ³ ; <50.0 – 25.0 x 10 ⁹ /L	<25,000/mm ³ ; <25.0 x 10 ⁹ /L	-
Serum amylase increased	>ULN - 1.5 x ULN	>1.5 - 2.0 x ULN	>2.0 - 5.0 x ULN	>5.0 x ULN	-
Sodium (Hypernatremia)	>ULN – 150 mmol/L	>150 – 155 mmol/L	>155 – 160 mmol/L	>160 mmol/L	-
Sodium (Hyponatremia)	<LLN – 130 mmol/L	-	<130 – 120 mmol/L	<120 mmol/L	-
Urate	>ULN – 10 mg/dL (0.59 mmol/L) without physiologic consequences	-	>ULN – 10 mg/dL (0.59 mmol/L) with physiologic consequences	>10 mg/dL; >0.59 mmol/L	-
White blood cell	<LLN – 3000/mm ³ ; <LLN – 3.0 x 10 ⁹ /L	<3000 – 2000/mm ³ ; <3.0 – 2.0 x 10 ⁹ /L	<2000 – 1000/mm ³ ; <2.0 – 1.0 x 10 ⁹ /L	<1000/mm ³ ; <1.0 x 10 ⁹ /L	-

LLN=lower limit of normal range; ULN=upper limit of normal range.
